### 2.3.2 Exclusion Criteria for Enrollment

1. Receipt of any blood product in past 120 days.
2. Psychiatric or cognitive illness or recreational drug/alcohol use that in the opinion of the principal investigator, would affect subject safety and/or compliance.

---

 Moderate symptoms are rated by the participant as moderate and may interfere with normal daily activities; [https://ctep.cancer.gov/protocoldevelopment/electronic\\_applications/ctc.htm#ctc\\_50](https://ctep.cancer.gov/protocoldevelopment/electronic_applications/ctc.htm#ctc_50)

 <https://www.cdc.gov/coronavirus/2019-ncov/need-extra-precautions/groups-at-higher-risk.html>

 Nasal cannula permitted for inclusion in study

3. Confirmed or self-reported presumed COVID-19, with symptoms that began more than 7 days prior to enrollment, and SARS-CoV-2 ID NOW or PCR positive sample that was collected more than 7 days prior to anticipated infusion for an asymptomatic participant or more than 10 days prior to anticipated infusion for a patient with mild to moderate symptoms at screening.
4. Symptoms consistent with COVID-19 infection that are more than moderate (as defined above) at time of screening.
5. Symptoms that have worsened in the period between screening and enrollment such that the subject is deemed to be medically unstable on the day of planned enrollment.
6. History of allergic reaction to transfusion blood products
7. Inability to complete infusion of the product within 48 hours after randomization.
8. Resident of a long term or skilled nursing facility
9. Known prior diagnosis of IgA deficiency
10. Participation in another clinical trial of anti-viral agent(s) for COVID-19

### **2.3.3 Recruitment Process:**

Recruitment for this protocol will involve approaching two groups of subjects: 1) patients with confirmed COVID-19 (asymptomatic or mildly to moderately symptomatic) and 2) patients with suspected COVID-19 (asymptomatic or mildly to moderately symptomatic).

#### **2.3.3.1 Recruitment Process for Confirmed & Suspected COVID-19 Patients**

Patients (including healthcare workers) who are asymptomatic or have mild to moderate symptoms (see Section 2.3.1.5) and have confirmed OR suspected COVID-19 will be approached by study staff, in-person, to introduce the study and see if they are interested in participating. Study staff may opt to phone potential participants after the ID NOW or PCR result becomes available to complete the assessment of eligibility and schedule the screening visits.

#### **2.3.3.2 Pre-Screening Potential Participants**

Potential participants will be approached by study staff and introduced to the study. The study staff will ascertain whether:

1. the potential subject has interest in the study and is willing to be screened, AND

2. the potential subject has had recent close contact with a COVID-19 case (see Section 2.3.1.2) or has recent self-reported or documented evidence of infection by nasal swab ID NOW or PCR that is positive for SARS-CoV-2, AND
3. the potential subject is at risk for severe COVID-19 disease based on age and/or their medical co-morbidities (see Section 2.3.1.6), AND
4. the potential subject is currently asymptomatic or minimally or moderately symptomatic of COVID-19 disease

Potential subjects who meet the above criteria and have a risk score for COVID-19 [0 risk if on supplemental oxygen at enrollment; otherwise  $\geq 1$  risk] will be invited to attend a screening visit at the site within the next 1-2 business days.

After the study is explained in detail, written consent will be obtained, and screening questionnaires, locator forms and required lab work will be completed. Those who provide consent will be eligible to enroll in the study when their screening nasal swab is positive for SARS CoV-2.

**Table: Schedule of Events**

Study period	Screen	Baseline	Infusion	Follow up						
Day	-1 to 0	0	0	1	3±2	7±1	14±3	28±7	60±7	90±7
Eligibility										
Informed consent	x									
Demographic and Medical history	x									
COVID-19 symptom screen	x		x							
SARS-CoV-2 ID NOW and RT-PCR obtained for eligibility	x 									
Pregnancy test 	x									
ABO 	x									
Study Drug Administration										
Randomization		x								
Drug infusion			x							
Study Procedures										
COVID-19 Symptom screen	x		x	x	x	x	x	x	x	
Other symptoms screen	x		x	x	x	x	x	x	x	
Concomitant medications	x		x	x	x	x	x			
Vital signs	x		x 		x	x	x			
Targeted physical examination	x		x			x	x			

 A repeat ID NOW and PCR at screening is required for all participants. However, for participants with documented evidence of infection by nasal swab PCR that is positive for SARS-CoV-2 in the prior week, a positive swab is not required to enroll the participant since they were already positive in the past week and will be tested by PCR during the Infusion Visit. At screening, two swabs will be collected from each participant, one for ID NOW (or comparable rapid antigen test) and one for a PCR-based test. If ID NOW is positive, it will not be necessary to wait for the PCR based test result to confirm the positive. If the ID NOW is negative, it will be necessary to wait for the PCR test result: PCR negative will mean individual is not eligible and PCR positive will mean they are potentially eligible if all the other inclusion criteria are met.

 Urine pregnancy test for women of childbearing potential

 Assessment of ABO type on file; requires two tubes of blood drawn 5 minutes apart, as per NYP Blood Bank procedures

 Vital sign testing: Immediately prior to infusion, 10-20 minutes after start of infusion, at completion of infusion and 15-60 minutes after the end of the infusion

Study period	Screen	Baseline	Infusion	Follow up						
Day	-1 to 0	0	0	1	3±2	7±1	14±3	28±7	60±7	90±7
Assessment of composite outcome of disease severity 			x	x	x	x	x	x	x	
Adverse event monitoring			x	x	x	x	x	x	x	
Laboratory testing										
CBC and CMP 	x					x	x			
SARS-CoV-2 RT-PCR 	x		x		x	x	x	x		
SARS-CoV-2 antibody	x				x	x	x	x		x
Blood for future testing	x				x	x	x	x		
Viral culture 	x				x					
Blood for PBMC for future testing	x									

### 2.3.4 Subject Withdrawal

1. Subjects can terminate study participation and/or withdraw consent at any time without prejudice.
2. Randomized subjects who withdraw from the study will not be replaced.
3. The investigator may withdraw subjects if they are non-compliant with study procedures or if the investigator determines that continued participation in the study would be harmful to the subject or the integrity of the study data
4. Discontinuation of the study: The study sponsor, FDA and IRB all have the right to terminate this study at any time

### 2.3.5 Stratified Randomization

1. Subjects enrolled in the study will be stratified and randomized using an interactive web- based system

 Assessment evaluates whether subject has shifted from “no clinical or laboratory evidence of COVID-19 infection to any of the composite outcomes of disease severity

[figure not shown]
 Comprehensive metabolic panel

 Nasal swab

 Includes sequencing for viral variants

 10 % sample of the nasal swabs

2. Subjects will be stratified by steroid administration (prior oral or IV steroids within prior 2 weeks at time of enrollment or prior inhaled steroids within prior 24 hours at time of enrollment) and by vaccination status (prior COVID-19 vaccine at time of enrollment) and then randomized in a 2:1 ratio to either CP or albumin 5%

### 2.3.6 Intervention

- I. Subjects will be randomized within each population in a 2:1 ratio to receive anti-SARS-CoV-2 plasma versus control (albumin 5%).
- II. Study drug: The investigational product is anti-SARS-CoV-2 plasma. Patients identified as having recovered from COVID-19 will serve as potential donors. Testing will confirm presence of anti-SARS-CoV-2 antibody prior to donation. Plasma donors will be screened for transfusion-transmitted infections (e.g. HIV, HBV, HCV, WNV, HTLV-I/II, *T. cruzi*, ZIKV) and plasma will be collected using apheresis technology. This is similar to standard blood bank protocols.
- III. Active arm will receive 2 units (200 – 250 mL each, 400-500 mL total) of anti-SARS-CoV-2 plasma from the same donor. These units have been verified to have a neutralizing titer of 1:320 each.
- IV. Control arm will receive 2 units of 250mL (500 mL total) of albumin 5%
- V. Both active and control drugs will be in standard plasma unit bags, with a study-specific ISBT label with the statement, “Caution: New Drug-- Limited by Federal (or United States) law to investigational use.”

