**Study Agent:**

- Anti-SARS-CoV-2 plasma: convalescent plasma (2 units of ~200-250 mL, total 400-500 mL) collected by apheresis from a volunteer who recovered from COVID-19 disease (collection and qualification covered by IRB protocol AAAS9845 [Convalescent plasma donors]))
- Control (albumin 5%): 2 units of 250mL, total 500 mL

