### **1.4. Albumin (Human) 5% as Control Study Product**

Participants randomized to the control arm will receive albumin (human) 5% infusion. The albumin will be prepared in bags that are as similar as possible to the bags used for plasma. The similar appearance of albumin and plasma will facilitate maintaining the blinded status of subjects and most of the study staff. Saline

solution or standard of care (no intervention at all) would not allow the subjects to remain blinded and if not blinded, subjects who receive convalescent plasma may alter their behavior, resulting in additional exposure to SARS-CoV-2 and risk of COVID-19.

While normal plasma is only very rarely associated with adverse reactions such as febrile, allergic, anaphylactic and hemolytic events, the risks of albumin infusions are even less frequent. Albumin infusions are rarely associated with rigors, hypotension/decreased BP, tachycardia/increased heart rate, pyrexia, feeling cold (chills), nausea, vomiting, dyspnea/bronchospasm, rash/pruritus as per the package insert. The risk of an anaphylactoid reaction to albumin is not described in the package insert but was observed with only 0.01% of over 60,000 units of infused albumin [Gales BJ and Erstadt BL, 1993]. Since then, the purification methods for albumin have improved even further. There is no risk of an ABO mismatch with albumin. The main risk of albumin infusion, as with plasma, is related to the risk of rapid volume expansion. The risk of volume overload will be mitigated by transfusing study product (CP plasma or albumin) over a 1- to 4-hour period, at the clinician's discretion, depending on the subject's medical history and clinical status.

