#### **2.4.3 Control arm**

The control (albumin 5%) will be prepared by the Brazil Research Pharmacy in bags that are identical to the bags used for plasma.

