#### **2.4.4 Rationale for dosing**

We will infuse 2 units (200-250 mL each, 400-500 mL total) of plasma with an anti-SARS-CoV-2 antibody  $\geq 1:320$  and 2 units of 250mL of albumin 5%, 500 mL total. Assuming a plasma volume of 3,500 ml, 500 ml of plasma with an antiviral titer of 1:320 would yield a final antiviral titer of 1:45. Dosing is based on a previous report wherein convalescent plasma therapy showed efficacy in COVID-19 patients following infusion of 200ml of convalescent plasma with a titer of 1:640 (Duan et al., 2020). We have not been able to identify sufficient numbers of plasma units with this titer to conduct this trial. Hence, we will employ two units with neutralizing titers of  $\geq 1:320$ .

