  - For these patients, the potential risk of a recurrence of volume overload will be mitigated by infusing the plasma or albumin (a total of 400-500 mL) more slowly, i.e., over 2 - 4 hours.

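### Albumin is specified at 500 mL and plasma at 400-500 mL, with no masking of fill volume, so a dispensed total clearly below 500 mL can point to plasma

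*Combined protocol and SAP*

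**What the plan says.** Three places give the same pair of volumes:

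- Protocol Summary, Study Agent: plasma is "convalescent plasma (2 units of ~200-250 mL, total 400-500 mL", and the control line is "Control (albumin 5%): 2 units of 250mL, total 500 mL".
- Section 2.3.6: "Active arm will receive 2 units (200 – 250 mL each, 400-500 mL total) of anti-SARS-CoV-2 plasma from the same donor", against "Control arm will receive 2 units of 250mL (500 mL total) of albumin 5" per cent.
- Section 2.4.4: the plasma range again, with "2 units of 250mL of albumin 5%, 500 mL total" for the control.

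Section 4.2 differs. For patients recovering from volume overload it speaks of "infusing the plasma or albumin (a total of 400-500 mL) more slowly", which applies the range to both products.

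On masking, section 2.4.3 says that the control "will be prepared by the Brazil Research Pharmacy in bags that are identical to the bags used for plasma". Section 2.3.6 adds that both products go into standard plasma bags with a study label. Section 1.4 relies on how the products look: "The similar appearance of albumin and plasma will facilitate maintaining the blinded status of subjects and most of the study staff". None of these statements mentions how full the bags are. Nothing in the document describes bag covers, volume matching or restricted access to volume records.

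**The concern.** Section 1.4 gives blinding as the reason for using albumin. It rejects saline and no treatment because subjects would then know their arm and might behave differently. A volume that can vary in one arm but not in the other works against that choice, and the cue is avoidable.

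The outcomes most exposed to knowledge of the arm are those that involve judgment: symptom reporting, the decision to hospitalize, and the on-site investigator's call on whether an adverse event is associated with study product (section 6.7). That call feeds two of the halting criteria in section 7.3. The documents do not say whether the people who make these judgments see the bags, so this is possible exposure and not demonstrated bias.

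**Working it through.** **Inputs**

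- Plasma: 2 units of 200 to 250 mL, from one donor (section 2.3.6).
- Albumin: 2 units of 250 mL (Protocol Summary, sections 2.3.6 and 2.4.4).
- Plasma collection target: about 450 to 600 mL, divided into units of 200 to 250 mL (section 2.4.2).
- Albumin fill tolerance per bag, t: not stated. It is an assumption here, shown from 0% to 20%.

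**Step 1. The plan's own totals.** Plasma: 2 x 200 = 400 mL to 2 x 250 = 500 mL. Albumin: 2 x 250 = 500 mL. Both agree with the text. The nominal gap is 250 - 200 = 50 mL per bag at most, or 100 mL per subject (100/500 = 20%).

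**Step 2. Which plasma totals the collection text supports.** Halving a 450 mL collection gives 2 x 225 = 450 mL, and halving 500 mL gives 2 x 250 = 500 mL. A two-way split of an at-target collection, kept within the unit limit, therefore gives 450 to 500 mL. A total near 400 mL needs something else, such as a three-way split of 600 mL (600/3 = 200 mL per unit, two units given) or a collection below target. The volume range permits 400 mL, but the text does not show it to be usual.

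**Step 3. When a low total points to plasma.** If both albumin bags sit at the bottom of the tolerance, the lowest albumin total is 500 x (1 - t). Only plasma can give a total below that. With L as the lowest plasma total, the plasma-only window is 500 x (1 - t) - L, or zero if that is negative.

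| Assumed t | Lowest albumin total | Window, L = 450 mL | Window, L = 400 mL |
|---|---|---|---|
| 0% | 500 mL | 50 mL | 100 mL |
| 5% | 475 mL | 25 mL | 75 mL |
| 10% | 450 mL | 0 | 50 mL |
| 15% | 425 mL | 0 | 25 mL |
| 20% | 400 mL | 0 | 0 |

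The window closes at t = 1 - L/500. That is 1 - 450/500 = 10% for at-target two-way splits, and 1 - 400/500 = 20% in the extreme case. Both thresholds are approximate, because the Study Agent entry marks the plasma range as approximate and 200 mL is not a hard floor.

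**Step 4. Direction.** Both arms can reach 500 mL, so a total of 500 mL identifies neither arm. The argument concerns dispensed volume only: an infusion of either product that is stopped early (sections 2.5 and 7.3) can also end below 500 mL infused.

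**Step 5. Cost of matching.** At 5 g per 100 mL, 500 mL of albumin 5% holds 25 g and 400 mL holds 20 g, a difference of 5 g.

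**The case against.** The best reply starts from section 4.2. If 400 to 500 mL for either product is what is done, then 250 mL elsewhere is a nominal unit size and the cue does not exist; the defect is only inconsistent wording. The documents do not rule this out. But the remark in section 4.2 is a parenthesis about slower infusion and sets no fill rule, whereas three other places state 250 mL per unit. If the range is what the sponsor intends, those three places need the same edit.

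Second, section 2.4 says that it only summarizes product matters for context, and the sentence on albumin preparation falls under it. A pharmacy procedure could deal with fill volume. This stands as a limit: the point is about the stated plan, not about what happened in practice. It is not a full answer, because the Protocol Summary and section 2.3.6 lie outside that summary.

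Third, the chain to harm has several unknown links: how many plasma totals fall well below 500 mL, how tightly albumin is filled, and whether a blinded person both sees the bags and knows the specification. Section 1.4 promises blinding only for subjects and most staff, so those who hang the bags may be unblinded by design. Each subject receives one product, with no side-by-side comparison. Infusion time adds little, because the rate is at the physician's discretion. All of this stands, and it keeps the point minor.

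A reader might go further and infer that a given share of plasma recipients can be identified, or that the go decision is biased. The documents support neither. They give no distribution of plasma fill volumes, so any share would be a guess. Several features also limit the effect on the endpoint:

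- Follow-up PCR results are withheld from subjects and the clinical team (section 1.5).
- Death and ventilation are hard outcomes.
- Table 2 places nobody in category 2 in either arm of either planning scenario, so the planned comparison does not turn on whether a PCR-positive outpatient reports symptoms.
- Follow-up may be done by visiting nurses (section 4.3), or by phone or telemedicine (note after section 4.10), so the Day 28 assessor need not have attended the infusion.

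**Conclusion.** The point holds as a minor one, with medium confidence. The Protocol Summary and sections 2.3.6 and 2.4.4 specify 500 mL of albumin against 400 to 500 mL of plasma, section 4.2 is not consistent with them, and no stated masking measure covers fill volume. If albumin is filled to 250 mL per bag, a dispensed total clearly below 500 mL is a one-way cue to plasma. A total just under 500 mL is weak evidence, because volumes are nominal.

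The size depends on two things that the documents do not give: the albumin fill tolerance and the spread of plasma fill volumes. The cue is gone at about 10% tolerance if plasma totals run from 450 to 500 mL; 20% applies only to the extreme of a 400 mL total. How often the cue would arise is unknown. Its effect on the primary endpoint is also unknown and, given the safeguards listed above, probably small. No effect on the go decision is claimed.

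**What to change.** In the Protocol Summary (Study Agent) and sections 2.3.6 (item IV), 2.4.3 and 2.4.4, state that the Brazil Research Pharmacy fills albumin bags to 200-250 mL each, 400-500 mL in total, matched to the fill volumes of the plasma units in stock. This also brings those sections into line with section 4.2.

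The cost is a wording change, a fill instruction to a pharmacy that already prepares these bags, and slightly more handling. Some controls would receive up to 100 mL less albumin solution (20 g of albumin instead of 25 g). Sample size, alpha, power and the analysis are unchanged.

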## 2.4 Study Product Considerations

The preparation of the anti-SARS plasma will take place at the New York Blood Center and the CUIMC-NYPH Blood Bank will dispense the plasma products to Brazil sites. The plasma collection procedures are not part of this research protocol and are described in separate protocols, which has separate IRB approval (AAAS9845). The description below provides a summary of study product considerations as context.

#### **2.4.1 Collection**

Donors will be pre-qualified for blood donation via study procedures described in IRB protocol AAAS9845. This will ensure that all convalescent plasma units in the CUIMC-NYPH Blood Bank will have high titers of IgG. All activities pertaining to the collection and processing of plasma will take place at [New York Blood Center/NYBC]. NYBC is one of the largest independent, community-based, nonprofit blood centers in the United States. It is operational in multiple states i.e. it is not confined to New York. NYBC has a longstanding research program and is well versed in the regulatory and ethical aspects of research, including clinical trials. The organization is FDA-licensed to produce convalescent plasma and AABB (American Association of Blood Banks) accredited, attesting to robust quality oversight of all operations.

#### **2.4.2 Collection and processing**

- Standard apheresis plasma collection will be performed per routine standard operating procedure at the collection facility (NYBC).
- As per routine practice, samples will be collected at time of donation for testing for transfusion-transmissible infections (all donors), ABO and red cell antibodies (all donors) and HLA antibodies (female donors with prior pregnancies).
- Target collection volume: ~450-600mL; this will allow for later splitting (separation) into 200-250mL daughter units.
- The plasma will be processed per routine practice; it will be frozen within 24 hrs of collection per AABB standards.
- The plasma will be maintained in quarantine at the blood center pending laboratory test results (i.e. infectious screening, ABO and RhD status, Red cell and HLA antibodies).
- If laboratory testing is acceptable (i.e. negative infectious and antibody screening), the products will be distributed to hospital blood bank for storage.
- In the event of an abnormal test result, the product will be discarded and the donor will be notified by the blood center as is standard practice.

#### **2.4.3 Control arm**

The control (albumin 5%) will be prepared by the Brazil Research Pharmacy in bags that are identical to the bags used for plasma.

#### **2.4.4 Rationale for dosing**

We will infuse 2 units (200-250 mL each, 400-500 mL total) of plasma with an anti-SARS-CoV-2 antibody  $\geq 1:320$  and 2 units of 250mL of albumin 5%, 500 mL total. Assuming a plasma volume of 3,500 ml, 500 ml of plasma with an antiviral titer of 1:320 would yield a final antiviral titer of 1:45. Dosing is based on a previous report wherein convalescent plasma therapy showed efficacy in COVID-19 patients following infusion of 200ml of convalescent plasma with a titer of 1:640 (Duan et al., 2020). We have not been able to identify sufficient numbers of plasma units with this titer to conduct this trial. Hence, we will employ two units with neutralizing titers of  $\geq 1:320$ .

### **2.5 Study drug administration**

- Drug will be administered within 48 hours (24 hours if possible) of randomization
- Infusion rate  $\leq 250$  mL/hour at physician discretion
- Pretreatment to minimize transfusion reactions (e.g. acetaminophen, diphenhydramine) will not be given, but will be available as needed to treat fever or allergic reactions. For severe allergic reactions corticosteroids (e.g., 125 mg methylprednisolone IV or comparable) may be used. For rare severe anaphylaxis, epinephrine will be available.
- If an AE develops during infusion, the infusion may be slowed or stopped as per investigator's decision.
  - Most reactions to plasma are relatively minor and the infusion can generally be continued. Infusion site burning and non-allergic systemic effects can generally be managed with slowing of the infusion. Infusion is generally stopped in cases of itching; participant is treated and then infusion cautiously re-started.
  - Severe allergic reactions generally require discontinuation of the infusion. These include:
    - Respiratory compromise: dyspnea, wheezing, stridor, hypoxemia

- A decrease in systolic blood pressure to < 90 mmHg or >30% decrease from baseline or a diastolic drop of >30% from baseline.
- Tachycardia with an increase in resting heart rate to > 130 bpm; or bradycardia <40 that is associated with dizziness, nausea or feeling faint.
- Syncope
- Confusion
- Any other symptom or sign which in the good clinical judgment of the study clinician or supervising physician warrants halting the infusion. For example, the rapid onset of gastrointestinal symptoms, such as nausea, vomiting, diarrhea, and cramps, for instance, may be manifestations of anaphylaxis and may warrant an immediate halt prior to meeting full SAE criteria
- Concomitant medications used during the infusion will be documented on the CRF

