## **7.3 Halting Criteria for the Study**

The study enrollment and dosing will be stopped and an ad hoc review will be performed if any of the specific following events occur or, if in the judgment of the study physician, subject safety is at risk of being compromised:

1. Unexpected death of a dosed subject in relation to infusion
2. Occurrence of a life-threatening allergic/hypersensitivity reaction (anaphylaxis), manifested by bronchospasm with or without urticaria or angioedema requiring hemodynamic support with pressor medications or mechanical ventilation.
3. One subject with an unexpected SAE associated with study product.
4. Two subjects with a Grade 3 or higher toxicity for the same parameter associated with study product.
5. An overall pattern of symptomatic, clinical, or laboratory events that the DSMB consider associated with study product and that may appear minor in terms of individual events but that collectively may represent a serious potential concern for safety.
6. Any other event(s) which is considered to be a serious adverse event in the good clinical judgment of the responsible physician. This will be appropriately documented.

Furthermore, given that ADE may be an issue with convalescent antibody treatment, out of an abundance of caution we will monitor the number of subjects in each trial arm that progresses to an indication for need of mechanical ventilation. In monitoring the number of subjects that progresses to this stage, we will present these data to the DSMB masked so that they may objectively evaluate and determine whether they would like to be unmasked. After at least 50% of trial participants have accumulated follow-up, the number of subjects that progress to this stage will be presented to the masked DSMB and formally asked whether they (1) see a clinically meaningful difference between trial arms that trigger an unmasking of the

DSMB and (2) if so do they require a formal interim analysis. At any point should the DSMB asked to be unmasked and require a formal interim analysis, we will examine the difference in treatment arms for need for mechanical ventilation. This interim analysis will adjust for factors related to need for mechanical ventilation including age and presence of cardiopulmonary comorbidities.

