### **Halting Criteria/Rules for Subject Infusion**

Infusion of study drug will be halted if any of the following manifestations of anaphylaxis develop and will not be restarted:

- Skin or mucous membrane manifestations: hives, pruritus, flushing, swollen lips, tongue or uvula
- Respiratory compromise: dyspnea, wheezing, stridor, hypoxemia
- A decrease in systolic blood pressure to < 90 mmHg or >30% decrease from baseline or a diastolic drop of >30% from baseline.
- Tachycardia with an increase in resting heart rate to > 130bpm; or bradycardia <40 that is associated with dizziness, nausea or feeling faint.
- Syncope
- Confusion
- Any other symptom or sign which in the good clinical judgment of the study clinician or supervising physician warrants halting the infusion. For example, the rapid onset of gastrointestinal symptoms, such as nausea, vomiting, diarrhea, and cramps, for instance, may be manifestations of anaphylaxis and may warrant an immediate halt prior to meeting full SAE criteria

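### Section 2.5 restarts an infusion stopped for itching, but the subject-infusion halting rules bar restart after pruritus, and nothing says how to tell the two cases apart

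*Combined protocol and SAP*

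**What the plan says.** Section 2.5 (Study drug administration) leaves slowing or stopping an infusion for an adverse event to the investigator and then describes usual handling in two tiers. Among the more minor plasma reactions it says of itching: "Infusion is generally stopped in cases of itching; participant is treated and then infusion cautiously re-started". For the upper tier it says: "Severe allergic reactions generally require discontinuation of the infusion". The list that follows covers respiratory compromise, blood pressure falls, heart rate changes, syncope, confusion and a clinical-judgment item. It has no skin or mucous membrane item.

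The Halting Criteria/Rules for Subject Infusion, an unnumbered heading after section 7.3, are worded as mandatory: "Infusion of study drug will be halted if any of the following manifestations of anaphylaxis develop and will not be restarted". Their first item is "Skin or mucous membrane manifestations: hives, pruritus, flushing, swollen lips, tongue or uvula". The remaining items match the severe list in section 2.5.

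Section 7.3 itself has a study-level criterion that describes anaphylaxis: "Occurrence of a life-threatening allergic/hypersensitivity reaction (anaphylaxis), manifested by bronchospasm with or without urticaria or angioedema", requiring pressor support or mechanical ventilation.

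On infusion time, section 1.4 speaks of "transfusing study product (CP plasma or albumin) over a 1- to 4-hour period". Section 2.5 caps the rate at 250 "mL/hour at physician discretion".

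**The concern.** Pruritus is itching, so the same sign appears in one section with a restart and in another with a bar on restart. Whether to restart after a possible allergic sign is a safety decision made at the bedside. Staff who restart as section 2.5 describes may breach a mandatory halting rule, and the protocol gives them no means of knowing when that is so. Two sites could handle the same event differently and each cite the protocol.

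The question can arise in either arm. The itching sentence in section 2.5 concerns plasma, and section 1.4 lists among the rare albumin reactions "dyspnea/bronchospasm, rash/pruritus as per the package insert". The documents give no itching rates, so nothing is claimed about how often this would happen or about unequal dosing between arms.

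**Working it through.** **Restart after itching.** No arithmetic applies, so the texts are set side by side for a participant whose only sign is itching.

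| Question | Section 2.5 | Rules for subject infusion (after 7.3) |
|---|---|---|
| Is the sign named? | Yes, as itching | Yes, as pruritus |
| Stop? | Generally | Mandatory |
| Restart? | Yes, cautiously, after treatment | No |
| Severity, extent or accompanying sign required? | None stated | None stated; any one listed item suffices |
| Reference to the other text? | No | No |

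1. The two lists of serious signs agree except for the skin and mucous membrane item, which only the subject-infusion rules contain. They therefore diverge on the very sign for which section 2.5 describes a restart.
2. The clinical-judgment item that closes the subject-infusion rules adds reasons to halt. It gives no discretion to restart.
3. The study-level criterion in section 7.3 does not supply the missing distinction. It is a trigger for stopping the whole study after a life-threatening reaction with bronchospasm, and it mentions neither itching nor pruritus.
4. Not restarting may breach neither text, because section 2.5 is discretionary. Restarting as section 2.5 describes can breach the halting rule as written.
5. For signs on both lists, such as respiratory compromise, the two texts point the same way but differ in strength. Section 2.5 says discontinuation is generally required; the halting rules say the infusion stops and does not resume.

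**Infusion time (minor).** Inputs: plasma is two units of 200–250 mL, 400–500 mL in total, and albumin is two units of 250 mL, 500 mL in total (section 2.4.4); the cap is 250 mL/hour (section 2.5); the shortest time is 1 hour (section 1.4).

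- Shortest time at the cap = volume / cap: 400/250 = 1.6 h; 500/250 = 2.0 h.
- Rate if the total dose runs over 1 hour = volume / 1 h: plasma 400–500 mL/hour, or 400/250 = 1.6 to 500/250 = 2.0 times the cap; albumin 500 mL/hour, or 2.0 times the cap.
- Rate if the hour is per unit: 200–250 mL/hour, or 200/250 = 0.8 to 250/250 = 1.0 times the cap. There is then no conflict.

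Section 1.4 does not say per unit. Section 4.2 favours the total-dose reading: for patients with earlier volume overload it slows the infusion of the 400–500 mL total to 2–4 hours. If 1–4 hours were per unit, two units in sequence would already take 2 × 1 = 2 to 2 × 4 = 8 hours, and 2–4 hours would not be clearly slower. Also, 500 mL over 2 hours is 500/2 = 250 mL/hour, which equals the ordinary cap.

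**The case against.** The strongest reply is that the two texts address different events. Section 2.5 separates minor reactions from severe ones and puts itching with the minor. The halting rules are confined to manifestations of anaphylaxis, so isolated itching could fall under the first and pruritus within anaphylaxis under the second. The itching sentence is also hedged and sits under investigator discretion, so the halting rule could simply be taken to control.

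That reading is available, and it softens the conflict. It does not remove it. The halting rules make any single listed item sufficient, attach no qualifier to pruritus, and give no test for anaphylaxis. The severe list in section 2.5 has no skin item, so it does not say when itching stops being minor. No clause states which section takes precedence.

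Two narrower objections are fair. The difference in strength for the shared signs is a weaker point, since section 2.5 describes no restart for those signs. The infusion-time mismatch is a separate, minor matter: section 1.4 is background text that leaves the time to the clinician, and a per-unit reading would remove the mismatch.

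**Conclusion.** The concern holds. For itching as the only sign, the protocol describes a restart in one place and bars it in another, with no criterion, cross-reference or order of precedence to settle the matter. This rests on the ordinary meaning of pruritus and on reading the halting rules as written, where one listed item is enough. On the narrower anaphylaxis-only reading the direct contradiction eases, but the missing criterion remains.

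The text is wrong as written and should be corrected, because it governs a safety action taken in real time. The size is qualitative: no sample size, power or alpha changes. The infusion-time mismatch is 1.6 to 2.0 times the cap on the total-dose reading and nil on the per-unit reading. It is minor, because times of 1.6–2.0 hours or longer fit both statements.

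**What to change.** - Reconcile section 2.5 with the Halting Criteria/Rules for Subject Infusion so that one stated rule covers an infusion stopped for itching or pruritus. If isolated itching and pruritus within anaphylaxis are meant to be handled differently, state how staff tell them apart.
- Cross-refer the two sections.
- For the signs that both lists contain, reconcile the hedged wording of one section with the mandatory wording of the other.
- Minor: reconcile the short end of the time range in section 1.4 with the rate cap in section 2.5, check both against the 2–4 hours in section 4.2, and state whether the range is for the total dose or per unit.

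Which rule applies in each case is for the clinical team; none is proposed here. The cost is a protocol wording amendment and a memo to sites, with no statistical cost.
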